1 PROTOCOL SUMMARY

1.1 Synopsis

Title:	Analysis of the immune response to COVID-19 vaccination and outcomes in individuals with and without immune deficiencies and dysregulations
Study Description:	
This prospective cohort study will assess the pre- and post-vaccination immune responses in individuals with select immunodeficiencies and immune dysregulations compared to healthy volunteers who receive a coronavirus disease 2019 (COVID-19) vaccine, as well as any adverse events (AEs) experienced after vaccination. All required study visits for this protocol may be conducted remotely; in-person visits at the NIH are optional. Subjects who have not yet been vaccinated will undergo baseline blood sampling using finger stick microsamplers and/or venous blood draw within 7 days prior to receiving the vaccine. Additional samples will be requested from participants approximately 14-21 days after dose 1 and 21-28 days after dose 2 (if applicable). Optional samples may be collected at 6, 12, and 24 months post-vaccination. If subsequent booster doses are received while a participant is still on study, blood samples will again be requested approximately 28 days after each booster dose, through the 5th Covid-19 vaccine dose received, and then participants may proceed with the optional 6-, 12-, and 24-month follow-up sample collection. Participants who are able to attend in-person visits at NIH will have optional on-site blood draws 1 and 3 days after doses 1 and 2 (as applicable). Research evaluations will include baseline severe acute respiratory syndrome-coronavirus-2 (SARS-CoV-2) antibody titers to the spike (S), nucleocapsid (N), and receptor binding domain (RBD) proteins, to assess pre-vaccination SARS-CoV-2 exposure and evaluate responses to vaccination. Additional immune markers of interest may include presence of autoantibodies, transcriptomic profiling, T-cell receptor (TCR) repertoire, among others. Participants who only submit finger stick home microsamplers at the timepoints listed above will be evaluated for SARS-CoV-2 antibody titers and autoantibodies only. All subjects will be asked at baseline about prior COVID-19 diagnosis, symptoms, and severity, and will be asked additional questions at follow-up timepoints (including after additional booster doses) about vaccine AEs using standardized questionnaires.

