Primary Objective:	To characterize the immune response to COVID-19 vaccination among immunodeficient and immune dysregulated individuals compared to healthy volunteers.
Secondary Objectives:	
• To characterize the COVID-19 vaccine-associated AEs among immunodeficient and immune dysregulated individuals compared to healthy volunteers.
Exploratory Objectives:	
• Assess the relationship between prior SARS-CoV-2 infection and vaccine-induced immune response.• To characterize pre-vaccine COVID-19 disease prevalence and severity among immunodeficient and immune dysregulated individuals.• To assess induction, strength, and durability of T- and B-cell-specific immune responses to SARS-CoV-2 (as measured by frequency and diversity of SARS-CoV-2 specific T and B cell clonotypes and titers of specific antibody responses), and their correlation to the underlying immune deficiency/dysregulation.• To characterize autoantibodies present in immunodeficient and immune dysregulated individuals before and after COVID-19 vaccination.• To assess the incidence of post-vaccination breakthrough SARS-CoV-2 infection and to determine the SARS-CoV-2 virus genomic sequence in such cases.
Primary Endpoint:	Change in S and RBD immunoglobulin G (IgG) antibody titer from baseline to 14-21 days or 21-28 days (depending on vaccine manufacturer and platform) after vaccine dose 1, and 21-28 days after dose 2 and any subsequent doses (depending on vaccine manufacturer and platform).
Secondary Endpoints:	
• Incidence of vaccine-associated AEs experienced by immunodeficient individuals compared to healthy volunteers.
Exploratory Endpoints:	
• Characterization of post-vaccine immune response and AEs in patients with antibody evidence of prior SARS-CoV-2 infection• Pre- and post-vaccination incidence of COVID-19-associated symptoms experienced in individuals with immune deficiency/dysregulation who are positive for SARS-CoV-2 by serology or diagnostic polymerase chain reaction (PCR).• Characterize how various forms of immune deficiency or dysregulation impact generation, strength, and durability of T- and B-cell responses.

- Incidence of autoantibodies pre- and post-COVID-19 vaccination comparing individuals with immune deficiency/dysregulation to healthy volunteers.

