There is some literature regarding the immune response in individuals with inborn errors of immunity to vaccination, including inactivated or subcomponent vaccines like the influenza or *Haemophilus influenzae* type b vaccines,^{5,6} and live-attenuated vaccines such as the measles-mumps-rubella and varicella vaccines.⁷ Depending on the immunologic defect, vaccine immunogenicity can vary widely, leaving some immunodeficient individuals inadequately protected. For example, individuals with complement defects should produce B- and T-cells in levels relatively similar to that of healthy volunteers, while others, like those with Wiskott-

Aldrich Syndrome, produce antibodies but a weak or absent T-cell response, and those with common variable immunodeficiency are only capable of producing T-cells without antibody. Because of this complexity, it is necessary to obtain a comprehensive understanding of the immunologic response to vaccines to better understand both the level of cellular and humoral protection against COVID-19 and also their estimated contribution to herd immunity.

Unfortunately, individuals with immunodeficiencies are typically excluded from vaccine trials measuring immunogenicity and safety, as was the case for the COVID-19 vaccines currently authorized or approved for use in the United States. This creates a need to study AEs in immunodeficient people to determine the safety and tolerability of the COVID-19 vaccines, especially in light of concerning anaphylaxis episodes in a minority of people who were vaccinated against COVID-19,⁸ even though AEs in this group, specifically in individuals with impaired T-cell responses, are usually limited to live vaccines.

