3 OBJECTIVES AND ENDPOINTS

Objectives	Endpoints	Justification for endpoints
Primary		
To characterize the immune response to COVID-19 vaccination among immunodeficient and immune dysregulated individuals compared to healthy volunteers.	Change in S and RBD IgG antibody titer from baseline to 14-21 days or 21-28 days (depending on vaccine manufacturer and platform) after dose 1, and 21-28 days after dose 2 and any subsequent doses (depending on vaccine manufacturer and platform).	It is of interest to understand the changes in anti-SARS-CoV-2 antibody levels induced by vaccination in individuals with immune deficiency/dysregulation.
Secondary		
To characterize the COVID-19 vaccine-associated AEs among immunodeficient and immune dysregulated individuals compared to healthy volunteers.	Incidence of vaccine-associated AEs experienced by immunodeficient and immune dysregulated individuals compared to healthy volunteers.	It is of interest to understand the safety (by knowing the incidence of AEs) of COVID-19 vaccines in individuals with immune deficiency/dysregulation.
Exploratory		
Assess the relationship between prior SARS-CoV-2 infection and vaccine-induced immune response.	Characterization of post-vaccine immune response and AEs in patients with antibody evidence of prior SARS-CoV-2 infection compared to those without evidence of prior infection.	Because so many people have had SARS-CoV-2 infections prior to vaccination, it is of interest to understand whether this affects the immune response to vaccination.

To characterize pre-vaccine COVID-19 disease prevalence and severity among immunodeficient and immune dysregulated individuals.	Incidence of COVID-19-and associated symptoms experienced in individuals with immune deficiency/dysregulation who are positive for SARS-CoV-2 by serology or diagnostic PCR.	It is of interest to understand the incidence and clinical presentation of COVID-19 in individuals with immune deficiency/dysregulation, especially as COVID-19 is an inflammatory-mediated disease.

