healthy volunteers should be sufficient to detect a true difference in mean anti-RBD log-titer of 0.4 at day 29 with 90% power, or a true difference of 0.35 with 80% power, while controlling the type I error rate at $\alpha=0.05$. We would also expect the width of a 95% confidence interval for the difference in mean log- titers to be approximately 0.35 units. It is also useful to consider the minimum detectable standardized effect size, also shown below, as antibody responses to other vaccines may differ from responses to the Moderna vaccine. Continuing with our example, a sample size of 20 participants per arm would be sufficient to detect a 1.05 standard deviation difference with 90% power using a two-sided two-sample t-test while controlling the type I error rate at $\alpha=0.05$.

[figure not shown]

Figure 2. Sample size estimates for primary endpoint. **A)** Lines represent number of participations required in each group and the smallest detectable differences in mean log-titers using a two-sided two-sample t-test with either 80% or 90% power while controlling the type I error rate at $\alpha=0.05$. **B)** Widths of 95% confidence intervals for a difference in mean log-titers. **C)** Number of participants required in each group to detect differences in standardized antibody effect size using a two-sided two-sample t-test with either 80% or 90% power while controlling the type I error rate at $\alpha=0.05$.

While it is hard to generalize antibody responses across the many immune conditions in this study given the phenotypic heterogeneity between and within diseases, patients in the following groups would generally be expected to have poor antibody responses to vaccination:

- Defects of cellular and humoral immunity (n=20) (e.g. RAG, DOCK8, adenosine deaminase [ADA], nuclear factor-kappa B essential modulator [NEMO])
- Predominantly antibody deficiencies (n=40) (e.g. X-linked agammaglobulinemia [XLA], CVID, activated PI3K delta syndrome 1/2 [APDS1/2], Ras-related C3 botulinum toxin substrate 2 [RAC2], caspase recruitment domain-containing protein 11 [CARD11], gain-of-function [GOF])

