8.4 Statistical Analysis

Multiple sets of analyses will be done to characterize the immune response in each of the groups of participants with immune deficiency/dysregulation:

1. Within-group: Estimate the vaccine response at each timepoint relative to baseline within an immune deficiency/dysregulation group.
2. Longitudinal between-groups: Compare the vaccine response profiles of different groups at sampling times.
3. Adjusted analyses controlling for SARS-CoV-2 infection.

For symptoms: focus will be on estimation of the proportion of symptoms that are present or absent in these individuals. Variables will be presented by frequency distribution (e.g. frequency counts, percentages, and 95% confidence intervals). In addition, this study will be used as the basis for hypothesis generation to explore disease manifestations in individuals with different types of immune deficiency/dysregulation if the number of enrolled individuals allow.

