8.4.1 Analysis of the Primary Endpoint

Log transformed antibody measurements will be modeled within a mixed model repeated measures (MMRM) framework, which is a longitudinal mixed model with fixed effects for (categorical) timepoint, immune deficiency/dysregulation, and the interactions of timepoint with immune deficiency/dysregulation and timepoint with baseline measurement, along with possible adjustment other covariates, such as age and sex. In this framework, we also include correlated subject-level random effects for each timepoint to account for clustered data. This also allows us to estimate the correlation between antibody responses to the first and second doses of vaccine. MMRM models are an appropriate tool for assessing response profiles in longitudinal studies where missing data is expected and it is appropriate to assume that data are missing at random conditional on observable covariates.^{13,14} The previous sample size justifications based on two-sample t-tests are likely to be slightly conservative as we expect the MMRM framework to make more efficient use of the data. Models will either be fit using the 'nlme' package in R, or, if a Bayesian formulation is deemed to be preferable for the purpose of incorporating prior information, can be fit using the 'brms' and 'rstanarm' packages.

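### Identifying prior infection by antibody alone can make previously infected patients look like better vaccine responders when they are only better antibody makers

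*Combined protocol and SAP*

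**What the plan says.** Section 3 compares immune response and AEs "in patients with antibody evidence of prior SARS-CoV-2 infection compared to those without evidence of prior infection". The Synopsis (1.1) gives the same endpoint without a comparator: "Characterization of post-vaccine immune response and AEs in patients with antibody evidence of prior SARS-CoV-2 infection". The next exploratory endpoint in Section 3 uses a wider rule, taking people "who are positive for SARS-CoV-2 by serology or diagnostic PCR".

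The protocol expects antibody capacity to be uneven. Section 2.2 states that "those with common variable immunodeficiency are only capable of producing T-cells without antibody". Section 8.3 says that, "given the phenotypic heterogeneity between and within diseases, patients in the following groups would generally be expected to have poor antibody responses to vaccination".

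On analysis, Section 8.4 lists "Adjusted analyses controlling for SARS-CoV-2 infection" without defining infection. The model in Section 8.4.1 includes "interactions of timepoint with immune deficiency/dysregulation and timepoint with baseline measurement", but it is written for the primary endpoint.

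No antigen is named for the antibody evidence. The Synopsis has baseline titers to S, N "and receptor binding domain (RBD) proteins, to assess pre-vaccination SARS-CoV-2 exposure and evaluate responses to vaccination". The Section 1.2 footnotes and Section 4.1 also admit people who are already vaccinated and take their baseline sample before a booster.

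**The concern.** The classifier (antibody after infection) and the titer outcome (antibody after vaccination) share a cause: the capacity to make antibody. In a group that mixes better and poorer makers, infected patients who did not seroconvert are left out of the infected arm. Those whose infection was never documented enter the comparator; documented ones need not, since the comparator is people without evidence of infection. The seropositive arm then holds more better makers than the comparator does, and its post-vaccine titer is higher even if infection has no effect.

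The risk is that a higher titer in seropositive patients of, say, the antibody-deficient or combined groups is read as an effect of prior infection. If the infection-adjusted analyses in Section 8.4 use the same flag, they would miss infections mainly in poorer makers.

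A second gap arises in people vaccinated before baseline. If S or RBD antibody counted for them, vaccine antibody could pass for infection.

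**Working it through.** **Plan's own figures.** The documents give no figure for this comparison. The only titer-scale calculation, in Section 8.3 (anti-RBD, day 29, 20 per arm, two-sided alpha 0.05), reproduces when 0.38 is used as the SD: power is 0.900 at a difference of 0.4 and 0.810 at 0.35. It supplies none of the inputs below, which are all assumptions.

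**Notation.** c = share of better makers; p = share infected; s1, s0 = serology sensitivity in better and poorer makers; d1, d0 = share of infections documented by PCR or diagnosis; sp = serology specificity; g = titer gap between the two classes. There is no infection effect, and infection is unrelated to antibody capacity.

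Per class, before weighting by class share:
- Infected arm as written: A = p·s + (1−p)(1−sp)
- Comparator: C = p(1−s)(1−d) + (1−p)·sp
- Infected arm if documented infection also counts: B = p[1−(1−s)(1−d)] + (1−p)(1−sp)
- Spurious difference = g × (better-maker share of the arm − better-maker share of C)

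**Central case.** c = 0.5, p = 0.2, s1 = 0.9, s0 = 0.5, d1 = d0 = 0.5, sp = 1, g = 1 log10.

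| | Better | Poorer | Better-maker share |
|---|---|---|---|
| As written | 0.5×0.2×0.9 = 0.090 | 0.5×0.2×0.5 = 0.050 | 0.090/0.140 = 0.643 |
| Comparator | 0.5×(0.01+0.80) = 0.405 | 0.5×(0.05+0.80) = 0.425 | 0.405/0.830 = 0.488 |
| Broader | 0.5×0.2×0.95 = 0.095 | 0.5×0.2×0.75 = 0.075 | 0.095/0.170 = 0.559 |

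- As written: 0.643 − 0.488 = **+0.155 log10**. Broader: 0.559 − 0.488 = **+0.071**.
- Infections left out of the arm: 1 − 0.140/0.200 = 30% as written; 1 − 0.170/0.200 = 15% broader.
- At sp = 0.97 the differences are 0.134 and 0.064.

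**Reading of the comparator.** If every missed infection enters it, the bias is 0.643 − 0.477 = 0.166. If none does, it is 0.643 − 0.500 = 0.143. The effect does not depend on that reading.

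**Ranges.**
- c 0.3–0.8, p 0.1–0.4, s1 0.8–1.0, s0 0.2–0.8, equal documentation 0.3–0.8, sp = 1: 0 to 0.44 as written, 0 to 0.28 broader.
- Also allowing d0/d1 of 0.2, 0.6 or 1.0 and sp of 0.97 or 1: 0 to 0.46 and 0 to 0.42. The broader rule is worse at about 12% of these grid points (29% at ratio 0.2, 6% at 0.6, none at 1.0).
- Limit where poorer makers never seroconvert (s0 = 0, other inputs central): 1 − 0.405/0.855 = 0.526 as written; 0.095/0.145 − 0.474 = 0.181 broader.
- Uniform antibody capacity, or s1 = s0 with equal documentation: 0.

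**Uneven documentation (d1 versus d0), otherwise central.**
- 50% versus 30%: 0.161 as written, 0.112 broader.
- 50% versus 10%: 0.166 as written, 0.157 broader.
- Documented infection alone, against everyone undocumented: 0 if documentation is equal; 0.625 − 0.489 = +0.136 at 50% versus 30%; −0.136 at 30% versus 50%.

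**Change from baseline.** If seropositive patients start b log10 higher, the difference is 0.155 − b: −0.345 at b = 0.5 and −0.845 at b = 1.

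**Precision in a group of 40.** Seropositive 0.14×40 = 5.6; comparator 0.83×40 = 33.2. The 95% half-width is 1.96×SD×√(1/5.6 + 1/33.2), which is 0.45 at SD 0.5 and 0.90 at SD 1.0.

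**Antigen rule.** Let f be vaccinated before baseline, with S/RBD then positive in v = 0.95 of better and 0.50 of poorer makers, other inputs central. Uninfected people counted as infected: (1−p)·f·v per class. Infected people in the arm: p[1−(1−s)(1−f·v)] per class. At f = 0.25:
- Uninfected: 0.5×0.8×0.25×0.95 + 0.5×0.8×0.25×0.50 = 0.145.
- Infected: 0.0924 + 0.0563 = 0.1486.
- Uninfected share of the arm: 0.145/0.2936 = 49%.

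At f = 0.10 and 0.50 the share is 29% and 65%. Under the broader definition without an N rule the three shares are 25%, 45% and 62%.

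**The case against.** The strongest reply is that the upward bias is shown only for unadjusted post-vaccine level. The primary antibody endpoint is change from baseline, Section 8.4 estimates response relative to baseline, and Section 8.4.1 adjusts for it. For change, the figures above can turn negative. This stands as a limit. It is not a rebuttal, because the endpoint says only post-vaccine immune response and fixes neither measure. The group terms in Section 8.4.1 leave mixing within a group, and baseline adjustment was not modelled here. AE and T-cell outcomes are not covered.

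The second reply is that the remedy is small and imperfect. In a group of 40 the infected arm grows from 5.6 to 6.8 people, and the bias falls by about 0.08 against a half-width of 0.45 to 0.90. Testing history depends on who was tested, so the gain can vanish if poorer makers are less completely documented. All of this stands.

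Third, Section 4.1 plans receptor clonotyping and says it will help assess earlier exposure, and the infection adjustment in Section 8.4 is not restricted to antibody. Both are correct, but neither is written into this endpoint. The S/RBD problem arises only if those antigens are counted in known vaccinees; the plan does not say they are, and it does not rule it out.

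**Conclusion.** The concern holds in its conditional form. As written, the endpoint selects the infected arm on a trait that also drives post-vaccine titer. Where antibody capacity is mixed within a group, this can raise the titer level with no infection effect. The illustrative size is +0.155 log10 as written and +0.071 with the broader rule. The range is 0 to about 0.46 when serology finds 20–80% of infections in poorer makers, and the as-written figure is 0.53 in the limit where it finds none. All inputs are assumptions, so the actual size is not established. A group with uniform capacity has no such bias, and the sign is open for change from baseline.

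Priority is low. This is one exploratory endpoint in a hypothesis-generating study, sampling error in a group of 40 exceeds the central bias, and the primary endpoint definition is unaffected.

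**What to change.** For this endpoint and for the infection-adjusted analyses in Section 8.4:

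- Define prior infection as positive baseline serology or a documented PCR result or diagnosis, from the records and the baseline questionnaire.
- For anyone vaccinated before the baseline sample, count N antibody only, not S or RBD.
- Require the comparator to have none of these. Leave people with no pre-vaccination sample and no documented infection unclassified.
- Compare within immune group. Groups planned at 5–10 would hold about one seropositive person (0.14×5 = 0.7 to 0.14×10 = 1.4), so describe those only.
- Report results by source of evidence, with a sensitivity analysis using non-antibody sources alone. State whether clonotype data count as a source.
- For titer, report both post-vaccine level and change from baseline.

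The cost is the wording of one endpoint and one analysis line. Testing and diagnosis history (Sections 4.1, 5.7 and 7.2) and N antibody (Sections 1.1 and 1.2) are already collected.

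The change reduces the bias but does not remove it. The gain shrinks, and can vanish, if documentation is less complete in poorer makers. Untested or asymptomatic infections are still missed, and Section 4.1 itself anticipates muted symptoms. The N rule assumes that the vaccine received raises no N antibody, and N antibody may also be low in poorer makers.

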7.2 Clinical Evaluations

Medical and medication history: Subjects enrolled on a protocol at NIAID will have their clinical history extracted from the NIH Clinical Research Information System (CRIS) for complete review of medical and medication history, including review of vaccination history and SARS-CoV-2 testing and symptom history. The questionnaire (described below) will also elicit information about relevant medical history, including history of SARS-CoV-2 infection. Subjects not enrolled on another NIAID protocol will undergo standard medical and medication history review by questioning.

Venous blood draw: Blood will be collected by venipuncture for laboratory testing (section 1.2) and storage. If participants cannot be brought to the NIH CC due to the ongoing COVID-19 pandemic, individuals can choose to have blood drawn at a primary care provider, academic hospital laboratory, Quest Diagnostics, or through collaboration with the Immune Deficiency Foundation, as necessary. Samples collected at clinics or at Quest may be labeled with a coded identifier, gender, and date of birth, as required by the local facility. The amount of blood drawn for research purposes in pediatric subjects will not exceed 5 mL/kg in a single day or 9.5 mL/kg over any eight-week period, in accordance with the CC Medical Administrative Series Policy M95-9 Guidelines for Limits of Blood Drawn for Research Purposes in the Clinical Center. The amount of blood drawn from pregnant participants will not exceed 50 mL over any eight-week period.

Fingerstick blood collection: All participants will be provided with a microsampler kit and mailing supplies to collect an at-home blood sample by fingerstick and send it to the CC. The sample will be used for laboratory testing (section 1.2) and storage.

Saliva collection: All participants will be provided with saliva collection kits and mailing supplies to collect post-vaccination saliva samples to return to the CC.

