8 STATISTICAL CONSIDERATIONS

8.1 Study Hypotheses

This is an exploratory study to characterize the immune response and vaccine-associated AEs in individuals with a variety of immune disorders who receive COVID-19 vaccination, in addition to describing disease prevalence and severity among subjects previously infected with SARS-CoV-2 and whether this affects vaccine immune response. We therefore hope to generate and test a number of hypotheses, including but not limited to:

1. Assessing whether and which of the immune correlates measured for the primary, secondary and exploratory endpoints change significantly after vaccination from baseline, comparing the response among various immune deficiency/dysregulation conditions and healthy volunteers (longitudinal change in immune response).
2. Assessing whether and which of the immune correlates measured for the primary, secondary, and exploratory end-points are significantly different among various immune disorder subgroups and healthy volunteers (cross-sectional immune response).
3. Assessing whether the dose 1 antibody response is correlated with the dose 2 antibody response among various immune disorder subgroups and healthy volunteers.
4. Assessing the incidence of vaccine-associated AEs among various immune disorder subgroups and healthy volunteers.
5. Assessing the prevalence and severity of COVID-19 symptoms among various immune disorder subgroups and healthy volunteers.

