8.2 Patient Populations for Analysis

The numbers provided for each group are an estimated number to be enrolled for each immune deficiency/dysregulation sub-group:

1. Combined immunodeficiencies (n=50)
2. Predominantly antibody deficiencies (n=40)
3. Disorders of immune regulation (n=40-60)
4. Congenital defects of phagocyte number or function (n=40-60)
5. Defects of intrinsic and innate immunity (n=25-30)
6. Autoinflammatory disorders (n=20)
7. Complement deficiencies (n=5-10)
8. Bone marrow failure syndrome (n=5-10)

9. Subjects with inborn errors of immunity who have received hematopoietic stem cell transplantation or gene therapy (n=20-30)
10. Subjects with secondary immunodeficiencies, to include those who have received hematopoietic stem cell transplantation or gene therapy (n=30-50)
11. Healthy volunteers (n=120 [2:1 healthy to largest immunodeficiency group])

Healthy volunteers will be enrolled to be representative of binned-age groups and sex distribution of the immune deficient study population. Age bins will be (3-5], (5-12], (12-16], (16-25], (25-45], (45-65], and 65+.

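### One serology-or-PCR rule for past COVID-19 under-counts infection in antibody-deficient groups relative to other groups, and no planned analysis allows for it

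*Combined protocol and SAP*

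**What the plan says.** Section 3 states the exploratory objective "To characterize pre-vaccine COVID-19 disease prevalence and severity among immunodeficient and immune dysregulated individuals". Its endpoint is the incidence of COVID-19 and its symptoms in "individuals with immune deficiency/dysregulation who are positive for SARS-CoV-2 by serology or diagnostic PCR". The synopsis carries the same serology-or-PCR rule. Neither place varies it by disorder.

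On antibody production, Section 2.2 says that "those with common variable immunodeficiency are only capable of producing T-cells without antibody". Section 8.3 says that "patients in the following groups would generally be expected to have poor antibody responses to vaccination", and lists defects of cellular and humoral immunity (n=20) and predominantly antibody deficiencies (n=40), with CVID as one example in the latter.

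On comparison, Hypothesis 5 in Section 8.1 reads "Assessing the prevalence and severity of COVID-19 symptoms among various immune disorder subgroups and healthy volunteers". It contains no case definition.

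On virus testing, the study's own PCR is on optional saliva collected after vaccination (Sections 1.2, 4.1 and 7.2). Before vaccination there is only past testing. For participants on a NIAID protocol, Section 7.2 provides for record extraction "including review of vaccination history and SARS-CoV-2 testing and symptom history"; others give their history when questioned. Section 8.4 plans symptom proportions with 95% confidence intervals. It does not separate cases by how they were found.

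**The concern.** Serology registers antibody, and the infection only through it. Where antibody production is impaired, an infection that was never tested for may leave no serological trace and be counted as no COVID-19. The same infection in an antibody-competent participant would usually be counted. The sensitivity of the case rule therefore depends on the factor that the subgroup description is meant to examine.

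At stake is the reading of the subgroup results. A lower figure in antibody-deficient patients could be taken as fewer infections when it reflects a weaker detector. If past testing also followed symptoms, the cases that remain would look more symptomatic than the infections that occurred.

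**Working it through.** The documents give no prevalence, serology sensitivity, testing rate or power for this endpoint, so there is no stated figure to reproduce. Every rate below is an assumption, varied over a range.

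**Assumed inputs.** True prevalence is 20% in all groups. The asymptomatic share *a* is 20% or 40%. Serology sensitivity *s* is 0.9 in competent participants, 0 where no antibody is made (the protocol's account of CVID) and 0.3 for a poor responder. Past PCR finds a fraction *p* of symptomatic and *q* of asymptomatic infections. The two tests are treated as independent.

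**Formulas.**
- Detection if symptomatic: dS = 1 − (1 − s)(1 − p)
- Detection if asymptomatic: dA = 1 − (1 − s)(1 − q)
- Overall detection: D = (1 − a)·dS + a·dA
- Observed prevalence = 20% × D
- Observed symptomatic share = (1 − a)·dS / D

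**One case in full** (a = 0.4, p = 0.7, q = 0.1):
- s = 0.9: dS = 0.97, dA = 0.91, D = 0.582 + 0.364 = 0.946. Prevalence 18.9%, symptomatic share 62%.
- s = 0.3: dS = 0.79, dA = 0.37, D = 0.474 + 0.148 = 0.622. Prevalence 12.4%, share 76%.
- s = 0: dS = 0.70, dA = 0.10, D = 0.42 + 0.04 = 0.46. Prevalence 9.2%, share 91%.

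**Range** (observed prevalence / symptomatic share):

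| Past PCR (p/q), a | Competent, s = 0.9 | Poor, s = 0.3 | None, s = 0 |
|---|---|---|---|
| 0.5/0.2, a = 0.4 | 18.8% / 61% | 11.3% / 69% | 7.6% / 79% |
| 0.7/0.1, a = 0.4 | 18.9% / 62% | 12.4% / 76% | 9.2% / 91% |
| 0.7/0.1, a = 0.2 | 19.2% / 81% | 14.1% / 90% | 11.6% / 97% |
| 0.9/0.1, a = 0.2 | 19.5% / 81% | 16.4% / 91% | 14.8% / 97% |
| 0.3/0.3, a = 0.4 | 18.6% / 60% | 10.2% / 60% | 6.0% / 60% |
| 0.9/0.9, a = 0.4 | 19.8% / 60% | 18.6% / 60% | 18.0% / 60% |
| 1/1, a = 0.4 | 20.0% / 60% | 20.0% / 60% | 20.0% / 60% |

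The first four rows have symptom-driven testing; the last three do not. The prevalence gap appears in every row except complete testing. The shift in symptomatic share appears only in the first four.

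**Possible reversal of the symptom shift.** Suppose serology in competent participants also misses more silent infections (0.95 symptomatic, 0.75 asymptomatic), with p = q = 0.3 and a = 0.4. Then dS = 0.965, dA = 0.825 and D = 0.579 + 0.330 = 0.909. The symptomatic share is 0.579/0.909 = 64% in competent participants against 60% with no antibody.

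**Scale in this study.** In the 0.7/0.1, a = 0.4 case, a group of 40 yields 40 × 0.092 = 3.7 detected cases instead of 40 × 0.189 = 7.6. Against the 120 healthy volunteers of Section 8.2, power to declare that artefact significant is about 27%. The damage is mainly to the estimates.

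**The case against.** Five points can be made for the plan.

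- **The comparison with healthy volunteers is not explicit.** The endpoint row covers affected participants only, and Hypothesis 5 names no case rule. A reader might infer that the protocol compares infection prevalence with healthy volunteers under serology or PCR; no section says so. This stands, and that part of the point is conditional. The difference between antibody-deficient and antibody-competent disorders does not depend on it.
- **Serology is not blind across these groups.** A reader might infer that two whole groups make no antibody. The protocol says that of CVID only; the rest are expected to respond poorly to vaccination. This stands: s = 0 applies to part of one group, and a reduced value such as 0.3 is the fairer picture elsewhere.
- **More symptomatic disease is not built in.** A reader might infer that the rule itself makes these groups look more symptomatic. That needs symptom-driven past testing, which is plausible but not stated; without it the share is unchanged or slightly reversed.
- **Other evidence of exposure is planned.** Section 4.1 says receptor clonotypes will help assess exposure before vaccination. They are outside the endpoint definition and Section 8.4, and the synopsis limits microsampler-only participants to SARS-CoV-2 antibody titers and autoantibodies. This is a partial answer.
- **The consequence is modest.** The endpoint is exploratory and descriptive. This stands, and limits the point to a reporting change.

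**Conclusion.** The point holds as differential under-ascertainment of past infection in antibody-deficient groups. It rests on the protocol's own account of antibody production, the absence of study PCR before vaccination, and past PCR testing having been less than near complete.

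On assumed rates with 20% true prevalence and symptom-driven testing, observed prevalence is 7.6-14.8% with no antibody and 11.3-16.4% at serology sensitivity 0.3, against 18.8-19.5% in competent participants. It narrows to 18.0% against 19.8% if PCR found 90% of infections, and vanishes with complete testing. Enrichment for symptomatic cases is a conditional second effect: 79-97% against 61-81% over the symptom-driven range, and absent otherwise.

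The documents do not support reading the rule as making these groups more symptomatic by construction, or serology as uninformative in them. The primary analysis of titer change is unaffected.

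**What to change.** Add to Section 8.4:

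1. Keep the combined serology-or-PCR definition for description within each disorder group.
2. For each group, report virus-test-confirmed and serology-only cases in separate columns, with symptom proportions for each. Record whether the virus test was documented or self-reported.
3. Make any comparison between disorder groups, or with healthy volunteers, on virus-test-confirmed cases as a stated sensitivity analysis. Do not compare serology-based prevalence across groups that differ in antibody production.
4. State that in the antibody-deficient groups a negative serology is weak evidence of no infection. A positive result is not weakened for that reason.
5. State which case definition Hypothesis 5 uses.

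Replacing the definition outright with virus test only would go too far. With p/q = 0.7/0.1 and a = 0.4, every group would show 9.2% and 91% symptomatic: comparable, but far from the assumed 20% and 60%, and worse than the 18.9% and 62% that the combined rule gives in competent groups. Nor does it cure unequal testing. If competent participants were tested at 0.5/0.1 and antibody-deficient patients at 0.9/0.5, virus-test-only prevalence would be 20% × (0.6 × 0.5 + 0.4 × 0.1) = 6.8% against 20% × (0.6 × 0.9 + 0.4 × 0.5) = 14.8%, a gap in the other direction.

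The cost is analysis wording and a few table columns, using baseline serology, testing history and questionnaires already planned. The comparison will rest on fewer cases. Some participants can give only a reported test, and unequal access to testing remains a limit to state.
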